6.3.4. Activity Level Monitoring Endpoints

The Lower Extremity Activity Scale (LEAS) is an 18-point integer scale reflecting the subjects physical function status, ranging from 1 (bed bound) to 18 (competitive athlete).

The accelerometry endpoints of average daily minutes of physical activity, average daily physical activity counts, minutes of moderate to vigorous physical activity (MVPA), minutes of bouts MVPA, and average daily step count will be calculated from the raw data.

The Activity Level Monitoring endpoints are listed below:

- *Lower Extremity Activity Scale: change from Baseline to Weeks 4, 8, 16, 24, 56 and Week 80 (all subjects).*
- *Change from Baseline to Weeks 16 and 56 in average daily minutes of physical activity (a subset of subjects).*
- *Change from Baseline to Weeks 16 and 56 in average daily physical activity counts (a subset of subjects).*
- *Change from Baseline to Weeks 16 and 56 in average daily minutes of moderate to vigorous physical activity (a subset of subjects).*
- *Change from Baseline to Weeks 16 and 56 in average daily minutes of bouts (sustained) moderate to vigorous physical activity (a subset of subjects).*
- *Change from Baseline to Weeks 16 and 56 in average daily step count (a subset of subjects).*

09001776e193181b056ApprovedApproved On: 08-10-2019 08:56 (GMT)

A valid day of monitoring will be defined as 10 or more wear hours in a 24-hour period as verified from accelerometer output. During Screening, a complete monitoring period will be defined as containing at least 1 valid weekend day of data and a minimum of 4 valid days of monitoring. During activity level monitoring between Week 14 and the Week 16 visit and between Week 54 and the Week 56 visit, a complete monitoring period will be defined as containing at least 2 valid weekend days of data and a minimum of 8 valid days of monitoring.

For the purposes of the MVPA endpoints, the three intensity levels of activity are defined as light (100 – <1,500 counts), moderate (1,500 – <6,500 counts), and vigorous (≥6,500 counts). The data will be further summarized as total daily time (minutes) for each intensity level.

A “bout” of moderate to vigorous activity is defined as 10 or more consecutive minutes above the moderate physical activity level threshold, with allowance for interruptions of 1 or 2 minutes below the threshold.

The daily data for each endpoint will be calculated as indicated above. These daily scores will be used to calculate the score for Baseline, and Weeks 16 and 56 relative to the appropriate visit (ie, 7 days within the screening period for Baseline and 14 days prior to the Weeks 16 and 56 visits). All valid data will be used even if it exceeds the intended 7/14 days specified in the protocol.

6.4. Covariates

For all models analyzing the continuous primary and secondary efficacy endpoints (except rescue medication) the corresponding Baseline value will be used as a covariate, in addition to Baseline diary average pain. Study site will be fitted as a random effect in the ANCOVA models. The randomization stratification variables of index joint (hip or knee), NSAID cohort (celecoxib, naproxen and diclofenac), and highest Kellgren-Lawrence grade of any Hip/Knee joints (grade 2, 3 or 4) will be included as fixed effects.

A listing of subjects with mis-matches between the stratification variables entered at randomization and the case report form data (including central lab data for Kellgren-Lawrence grade) will be provided. In analysis models, the strata entered at randomization will be used, but for descriptive summarization of the population and identification of subgroups, the strata as indicated on the case report form data will be used.

For the models analyzing the amount and number of days of rescue medication use the model will include terms for Baseline WOMAC Pain, Baseline diary average pain and stratification factors.

The analysis of the incidence of treatment discontinuation due to lack of efficacy will include model terms for baseline WOMAC Pain subscale score, Baseline Diary Average Pain, index joint, Kellgren-Lawrence grade, NSAID group and treatment group.

0900177 (e-s) 1811656 Approved Approved On: 03-10-2019 08:56 (GMT)

For treatment response endpoints relating to WOMAC Pain and PGA, the Baseline WOMAC Pain and PGA values will be used respectively as covariates in the analysis model, in addition to the stratification parameters of index joint, highest Kellgren-Lawrence grade of any hip or knee joint, NSAID group and Baseline diary average pain. For the OMERACT response value, the Baseline WOMAC Pain subscale score will be used to represent the Baseline score covariate, in addition to the covariates named above (Baseline diary average pain, and the three stratification factors).

Additional analyses of the three co-primary endpoints will examine the treatment interactions with Study site and Country. Note, separate analyses will be performed for the individual NSAID groups.

The Baseline diary average pain is used in the analysis of most endpoints. However if a patient has a missing value for this covariate then to avoid exclusion of the patient for the endpoint then a Baseline value will be imputed as the patient's WOMAC Pain subscale score. This imputed value will not be used in the analysis of the Average Pain from the diary, but as a covariate for other endpoints.

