Serum Anti-tanezumab Antibody n		Х		Х		Х
Plasma Pharmacokinetic sample n		Х		Х		
Serum NGF (PD) sample n		Х		Х		
Serum and Urine Biomarkers n		X°		X o		X°
Synovial Fluid Sample		Option	nal for subjects undergo	oing arthrocentesis; add	itional sampling may be	needed t
Serum 25-hydroxy vitamin D and parathyroid hormone		*		X		

Visit Identifier	As soon as possible after determining	Early Termination Visit 1	Early Termination Telephone Contact 1 r	Early Termination Visit 2	Early Termination Telephone Contact 2 r	Early Termination Visit 3
subject will be discontinued from study	~8 Weeks after last SC dose	~12 Weeks after last SC dose	~16 Weeks after last SC dose	~20 Weeks after last SC dose	~24 Weeks after last SC dose	
Abbreviations: $\rightarrow$ = ongoing/continuous event; BP = Blood Pressure; ECG = electrocardiogram; HR = Heart Rate; HCRU = Health Care Resource Utilization; EC = ethics committee; EQ-5D-5L = EuroQol 5 Dimension; IRT = Interactive Response Technology; LEAS = Lower Extremity Activity Scale; mPRTI = Patient Reported Treatment Impact assessment-modified; MRI = Magnetic Resonance Imaging; NGF = Nerve Growth Factor; NIS = Neuropathy Impairment Score; NSAID = Non-Steroidal Anti-Inflammatory Drug; PD = Pharmacodynamics; SAS = Survey of Autonomic Symptoms; TSQM (v.II) = Treatment Satisfaction Questionnaire Medicine version II; WPAI:OA = Work Productivity and Activity Impairment Questionnaire: Osteoarthritis						

- a. The Screening period begins up to a maximum of 37 days prior to randomization and lasts a minimum of 14 or 21 days, allowing completion of the 2 or 3 week period of pre-randomization NSAID regimen stabilization (refer to Section 6.1.1 for additional detail regarding NSAID regimen stabilization). Prior to entering the IPAP, subjects must washout from prohibited pain medications for at least 5 half-lives or 48 hrs (which ever is greater). During the IPAP, diary entries (joint pain and rescue medication use) must be provided for a minimum of 3 days in the 7 days immediately preceding randomization.

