#### 7.1.2. Rescue Medication and Amount

Rescue medication use will be collected daily via IRT from the beginning of the IPAP to the Week 16 Visit. The dosage strength of the acetaminophen tablets/caplets/capsules will be captured. The subject should note the number of tablets/caplets/capsules of rescue medication taken during the last 24 hours.

Following the Week 16 visit up to the Week 80 visit and during the Early Termination Follow-Up Period for subjects who enter this phase of the study, the use of acetaminophen / paracetamol as rescue medication will be collected once weekly using IRT. The subject will record the number of days rescue medication was used and maximum number of tablets, capsules or caplets of rescue medication taken on any day in the past week.

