For the analysis of the rescue medication endpoints, missing data is imputed for daily missing scores first, and then the last available weekly score (after daily missing data is imputed) will be used for subsequent missing weekly scores, as described below. For the analysis of the rescue medication endpoints while subjects are still in the study any missing data will be imputed by carrying forward the last recorded daily data up to Week 16 (LOCF daily data). Imputation using the daily data will occur up to the end of the last week when the subject is in the study (see [Appendix 1.1](#) for definitions of the last study day in each week). For example if a subject discontinues on study day 10, then data up to the end of Week 2 will be imputed in this way. The weekly scores for the rescue medication endpoints can then be calculated for each week the subject is in the study. Rescue medication endpoints are summarized and analyzed using LOCF, and so the last weekly score for the rescue medication will be used for LOCF after the subject has discontinued from the study (note, imputation is taken from the last week with non-missing data and not necessarily from the last available study week, eg, if Week 8 is missing then Week 7 data can be used). The baseline observation will not be carried forward in the case where a post-baseline observation is not available for the LOCF imputation. In the example above, the subject who discontinued in Week 2 (Study Day 10) will have their Week 2 value used as the LOCF value for all Weeks 3-16. The BOCF imputation rule will not be used for the subject because rescue medication is collected during the Initial Pain Assessment Period only (days -7 to -1) and subjects should not be taking rescue medication within 24 hours of the Baseline visit (so part of day -1), therefore Baseline rescue medication use is not an accurate reflection of subjects' true Baseline use of rescue medication. Imputation of weekly diary data after Week 56 will not be performed.

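### The models for days and amount of rescue medication leave out the subject's own pre-dose rescue use, although it is recorded daily before randomisation

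*SAP*

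**What the plan says.** SAP section 6.4 gives the general rule and its exception in one sentence: "For all models analyzing the continuous primary and secondary efficacy endpoints (except rescue medication) the corresponding Baseline value will be used as a covariate". It then specifies the rescue models: "For the models analyzing the amount and number of days of rescue medication use the model will include terms for Baseline WOMAC Pain", followed by baseline diary average pain and the stratification factors. SAP sections 8.1.2, 8.2.2 (item 5) and 8.2.5 and protocol section 9.2.2 follow the same list, with no term for pre-dose rescue use. The incidence model in SAP section 8.2.5 has the same covariates.

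Pre-dose use is collected. Protocol section 7.1.2 states: "Rescue medication use will be collected daily via IRT from the beginning of the IPAP to the Week 16 Visit". Footnote a to the protocol's Schedule of Activities sets a minimum amount: "diary entries (joint pain and rescue medication use) must be provided for a minimum of 3 days in the 7 days" before randomisation.

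SAP section 7 comments on the quality of this measure when it explains why baseline observation carried forward is not used for rescue endpoints. It says that "rescue medication is collected during the Initial Pain Assessment Period only (days -7 to -1") and that "subjects should not be taking rescue medication within 24 hours of the Baseline visit (so part of day -1"), and concludes: "therefore Baseline rescue medication use is not an accurate reflection of subjects" true baseline use.

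**The concern.** In a randomised comparison, a pre-dose measurement of the outcome is often one of the more useful covariates. It cannot be affected by treatment, and it removes variation that baseline pain scores reach only indirectly, such as a person's habit of taking acetaminophen. Here the measurement exists for nearly every randomised subject and is left out. Section 6.4 gives no reason for the exception. The reason in section 7 answers a different question.

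At stake is precision in two secondary endpoints: number of days of use, analysed at nine time points from Week 2 to Week 56, and amount taken, analysed at Weeks 2, 4, 8 and 16.

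**Working it through.** The plan has no figure to reproduce. Protocol section 9.1 gives no power, standard deviation or effect size for rescue endpoints, and neither document gives a correlation between pre-dose and on-study use.

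**Step 1. Does the accuracy argument extend to a covariate?** Three places in the SAP suggest that it does not.

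- Baseline diary average pain comes from the same IPAP days (-7 to -1), using the last 3 available scores or fewer (SAP sections 6 and 7, Appendix 1.1). It is a covariate in these same rescue models.
- The accelerometry endpoints use the same model family, negative binomial, with their own baseline as a covariate (SAP section 8.2.2, item 12). That baseline needs only 4 valid days (SAP section 6.3.4).
- Section 7 describes the abstinence before the Baseline visit as touching only part of day -1. It precedes randomisation, so it applies to all arms alike.

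A carried-forward value becomes the subject's outcome, so error in it enters the estimate directly. A covariate only has to be associated with the outcome. Error in a pre-randomisation covariate weakens the gain but does not bias the treatment ratio in a log-link model.

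**Step 2. Possible gain for days and amount.** Let r be the partial correlation of IPAP rescue use with the outcome, given the covariates already in the model. This is an assumption. In the linear approximation:

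- variance ratio = 1 - r²
- cut in standard error (SE) = 1 - √(1 - r²)
- equivalent increase in sample size = 1/(1 - r²) - 1

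| r (assumed) | Cut in variance | Cut in SE | Equivalent extra subjects |
|---|---|---|---|
| 0 | 0% | 0% | 0% |
| 0.1 | 1% | 0.5% | 1.0% |
| 0.2 | 4% | 2.0% | 4.2% |
| 0.3 | 9% | 4.6% | 9.9% |
| 0.4 | 16% | 8.3% | 19.0% |
| 0.6 | 36% | 20.0% | 56.2% |

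**Step 3. Check in a negative binomial model.** This was an illustrative simulation with assumed parameters: two arms of 1000, 60 runs per setting, and a baseline pain term in both models. The measured baseline correlates at a set level with the subject's underlying propensity to use rescue. That is a different quantity from r, because the outcome is itself a noisy reading of the propensity.

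| Correlation with propensity (assumed) | SE without | SE with | Cut in SE | Cut in variance |
|---|---|---|---|---|
| 0.2 | 0.0595 | 0.0592 | 0.6% | 1 - (0.0592/0.0595)² = 1.0% |
| 0.4 | 0.0596 | 0.0581 | 2.6% | 1 - (0.0581/0.0596)² = 5.0% |
| 0.6 | 0.0598 | 0.0559 | 6.5% | 1 - (0.0559/0.0598)² = 12.6% |

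The mean log ratio barely moved: -0.199 to -0.201, -0.212 to -0.215 and -0.198 to -0.202, against a true value of -0.2. A noisy measure yields a small gain and no bias.

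**Step 4. Incidence is different.** It is analysed by logistic regression with odds ratios (SAP section 8.1.3). In an illustrative simulation (1000 per arm, 300 runs, conditional log odds ratio -0.3), the mean SE of the log odds ratio rose when a prognostic covariate was added: from 0.093 to 0.095, 0.092 to 0.101 and 0.091 to 0.109 as the covariate was made stronger. The estimate also moves away from zero, so power can rise. But the target becomes a different conditional odds ratio, and its interval need not narrow.

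**The case against.** The omission is deliberate and consistent. SAP section 6.4 names the exception, protocol section 9.2.2 lists the same covariates, and SAP section 7 records a measurement problem. A reader might infer that the term was dropped by oversight, or for no reason at all; the documents do not support that. What they lack is a reason that applies to a covariate.

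The link between pre-dose and later use may also be weak. Under protocol section 5.9, rescue before randomisation is taken as needed for osteoarthritis or other pain or illness. From Baseline to Week 16 it is limited to 3 days per week for osteoarthritis pain, and from Week 16 to Week 64 daily use is allowed. In the IPAP every subject takes an active NSAID; afterwards two of three arms take oral placebo with tanezumab. Three diary days are enough, yet days of use is analysed to Week 56. All this stands. It may lower r, perhaps close to zero at later weeks, but it cannot introduce bias, because the measure precedes randomisation.

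A reader might also infer that all three rescue endpoints now have needlessly wide intervals. Step 4 shows that this does not follow for incidence. Nor do the documents support a claim that many subjects' worth of information is lost: the larger entries in the Step 2 table rest wholly on an assumed r, which must be a partial correlation given the two pain terms already fitted.

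**Conclusion.** The point holds as a missed improvement for number of days and amount. The stated accuracy concern supports the no-carry-forward rule; it does not support leaving IPAP rescue use out of the covariates. The size is unknown. The variance falls by 4% or less if r is 0.2 or below and by about 9% to 16% if r is 0.3 to 0.4 (linear approximation). It falls less if the measure is noisy and probably less at later weeks. For incidence the term is optional.

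Severity is low. The present models are valid and the treatment ratios are not biased by the omission. These endpoints lie outside the error-controlled family (SAP section 4.2) and carry no power claim. A reader might take this as an error that puts the efficacy conclusions in doubt; nothing in the documents supports that.

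**What to change.** Before unblinding:

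- In SAP sections 6.4, 8.1.2, 8.2.2 (item 5) and 8.2.5, add two terms to the negative binomial models for days and amount: mean rescue use per day over the available IPAP diary days, and any IPAP use (yes/no). State a rule, blind to treatment arm, for the few subjects with no IPAP rescue entries.
- Keep the section 7 rule that baseline rescue use is not carried forward.
- Treat the term as optional in the logistic model for incidence. If it is added, say that the odds ratio is then conditional on it.
- If the sponsor prefers to keep the exception, state in section 6.4 a reason specific to covariates, or fit the adjusted model as a prespecified supportive analysis.

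The cost is a few lines of SAP text and programming. No new data are needed. Protocol section 9 lets the SAP modify planned analyses and calls for a protocol amendment only for major changes to the primary endpoint or its analysis, so none is required here.

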6.5. Subgroup Analyses

Separate tables will be produced for subjects in the ITT analysis set in Japanese sites. These tables will be defined prior to the unblinding of the study.

The accelerometry data is collected in the subset of subjects (the accelerometry analysis set), so analysis of these subjects will occur in this subset.

Analysis of tanezumab versus individual NSAID groups will occur in the individual NSAID cohort subsets.

7. HANDLING OF MISSING VALUES

The three co-primary efficacy endpoints are the changes from Baseline to Week 16 in the WOMAC Pain subscale, the WOMAC Physical Function subscale, and the Patient Global Assessment of Osteoarthritis. For Japan, the two co-primary efficacy endpoints are the change from Baseline to Week 16 in the WOMAC Pain and Physical Function subscales.

The primary analysis of the co-primary endpoints will use multiple imputation for missing data at Week 16 (where the method for imputation will be dependent on the reason for missing data) followed by the ANCOVA analysis with the model described below for the multiple imputed datasets. The imputation strategies are described in the following table. While the table describes the multiple imputation strategy specifically for the Week 16 time point, multiple imputation analysis at other time points will use the same strategy but with the appropriate time point, eg, 'Week 2' substituted for 'Week 16' in the table below. Efficacy data missing from windows after the Week 56 window, eg, Week 64, will not be imputed for any summary or analysis unless otherwise indicated.

0900177ea193181b656Approved\Approved On: 03-10-2019 08:56 (GMT)

Type of Missing Data	Imputation Method
Missing data resulting from discontinuation due to Death, Adverse Events (AEs) or Insufficient Clinical Response (Lack of Efficacy, LoE, including Patient meets protocol specified pain criteria for discontinuation) prior to or during the Week 16 visit reporting window*.	Multiple imputations will be created by sampling from a normal distribution based on the subject’s baseline score and the standard deviation (over all treatment groups) of the observed efficacy data at Week 16 over all ITT subjects. This is a multiple imputation version of BOCF single imputation method. [Seeds 1, 3, and 5 below].
Missing data for other reasons, ie, 
 • Subject did not discontinue on or before Week 16 (includes discontinuation for any reason after the end of the Week 16 visit reporting window*) • Subject discontinued for a different reason prior to or during the Week 16 visit reporting window*. 	Multiple imputations will be created by sampling from a normal distribution based on the subject’s last score and the standard deviation (over all treatment groups) of the observed efficacy data at Week 16 over all ITT subjects. For example if last observation for a subject is at Week 12, then the imputation sample for that subject is created using the subject’s Week 12 observation and the standard deviation of the Week 16 observations for all subjects. Note, a subject’s last observation may be the Baseline observation. This is a multiple imputation version of LOCF single imputation method. [Seeds 2, 4, and 6 below].

* See [Appendix 1.1](#) for a definition of the reporting windows.

The imputation of baseline-like data for subjects with missing data due to discontinuation due to Death, AE or LoE is intended to impute conservative efficacy values for those subjects who discontinue because of a reason that is considered to be a poor outcome for the subject, and so a poor outcome is imputed. For those subjects with missing data that is likely to not be related to treatment group, the intention is that missing data should be imputed based on a ‘missing at random’ assumption taking into account the subject’s previous available data.

One hundred imputed samples will be used in this analysis. In order to pre-define the analysis (and not to allow the results to change if run again), the following seeds will be used in the creation of the multiple imputed data: WOMAC scores [1] 7001-7100; and [2] 8001-8100; PGA scores: [3] 9001-9100 and [4] 10001-10100; and diary pain scores: [5] 11001-11100 and [6] 12001-12100. Imputed data for the PGA will be rounded to integer scores in the range 1 to 5. Imputed data for the WOMAC subscale and Average scores, and for the diary pain scores <0 and >10 will be truncated to 0 and 10, respectively. Imputed data for the WOMAC items of Pain when Going Up or Down Stairs and Pain when Walking on a Flat Surface will be rounded to integer scores in the range 0 to 10. The ANCOVA analysis described in [Section 8.1.1](#) (with covariates in [Section 6.4](#)) will be used for each imputation dataset, and the overall results will be calculated to take account of the variability both within and between imputation datasets using standard methods (Little & Rubin, 2002), which are described in [Appendix 3.2](#).

0900177ed1931781b0561ApprovedApproved On: 08-10-2019 08:56 (GMT)

This analysis will be used for the co-primary efficacy endpoints at Week 16, plus secondary analyses at other time points, and also for a range of secondary efficacy endpoints at all time points up to Week 56. When using the multiple imputation method described above for time points earlier than Week 56, then the reason for missing data is assessed up to the end of the window for that particular time point (see [Appendix 1.1](#)).

Three additional methods will explore the sensitivity of the effect of missing data. The first method of Baseline Observation Carried Forward (BOCF) for missing data at the primary time point of Week 16 will impute the subject's Baseline value for the Week 16 time point, and therefore a zero change from baseline. If a subject's baseline data is also missing then that subject's data remain missing for the post-baseline time point. The second method of Last Observation Carried Forward (LOCF) for missing data at the primary time point of Week 16 will impute the subject's last observed data value for the efficacy endpoint. With LOCF, if a subject is missing all post-baseline efficacy data for a given efficacy endpoint, then baseline will be carried forward (if baseline is missing then the subject would have no contributing data to be included in the analysis). In both the BOCF and LOCF imputation analyses, the same main effects ANCOVA model as described below will be used. The third method will use Mixed Model for Repeated Measurements (MMRM) utilizing all observed data up to and including Week 16, including data considered off-treatment (retrieved dropout; see [Appendix 1.1](#) for details on windows; if multiple observations are within a window, only the single observation selected for analysis by the windowing algorithm will be used in the MMRM analysis).

Analyses of the three co-primary measures at secondary time points will use the BOCF and LOCF imputation methods for missing data, and use the same (main effects) ANCOVA model as described for the primary analyses.

The responder endpoints will be analyzed using logistic regression for binary data, using both BOCF and LOCF separately for missing data of the response endpoint at a particular time point. Imputation using BOCF will lead to the subject being assessed as a non-responder. In addition, in order to closely match the primary imputation analysis, a mixed BOCF/LOCF imputation for response endpoints will be used. In this analysis BOCF imputation (ie, a subject would be a non-responder) would be used for missing data due to discontinuation for reasons of lack of efficacy (Insufficient clinical response on the end of treatment Subject Summary Case Report Form, and also including Patient meets protocol specified pain criteria for discontinuation), adverse event or death up to the time point of interest, and LOCF imputation would be used for missing data for any other reason.

Note, if Baseline is missing then the subject data for the change from Baseline will be set to missing for all efficacy analyses for that parameter. A subject who has a missing Baseline score will be missing for the response criteria for endpoints where the response is based on one parameter. The OMERACT-OARSI responder index is based on 3 parameters. It is set to missing if two or three out of these three parameters are missing at baseline (per its definition, a response can be still be achieved if only one parameter is missing, regardless of which one it is).

0900177ca193181b0561ApprovedApproved On: 08-10-2019 08:56 (GMT)

The individual WOMAC subscales are calculated as the mean of the individual items (5 for Pain, 17 for Physical Function and 2 for Stiffness). CCI

The WOMAC Average score is calculated as the mean of the three WOMAC subscale scores of Pain, Physical Function and Stiffness. CCI

Missing WOMAC subscale or WOMAC Average scores will be subject to the imputation method of the analysis as described above.

For the analysis of the rescue medication endpoints, missing data is imputed for daily missing scores first, and then the last available weekly score (after daily missing data is imputed) will be used for subsequent missing weekly scores, as described below. For the analysis of the rescue medication endpoints while subjects are still in the study any missing data will be imputed by carrying forward the last recorded daily data up to Week 16 (LOCF daily data). Imputation using the daily data will occur up to the end of the last week when the subject is in the study (see [Appendix 1.1](#) for definitions of the last study day in each week). For example if a subject discontinues on study day 10, then data up to the end of Week 2 will be imputed in this way. The weekly scores for the rescue medication endpoints can then be calculated for each week the subject is in the study. Rescue medication endpoints are summarized and analyzed using LOCF, and so the last weekly score for the rescue medication will be used for LOCF after the subject has discontinued from the study (note, imputation is taken from the last week with non-missing data and not necessarily from the last available study week, eg, if Week 8 is missing then Week 7 data can be used). The baseline observation will not be carried forward in the case where a post-baseline observation is not available for the LOCF imputation. In the example above, the subject who discontinued in Week 2 (Study Day 10) will have their Week 2 value used as the LOCF value for all Weeks 3-16. The BOCF imputation rule will not be used for the subject because rescue medication is collected during the Initial Pain Assessment Period only (days -7 to -1) and subjects should not be taking rescue medication within 24 hours of the Baseline visit (so part of day -1), therefore Baseline rescue medication use is not an accurate reflection of subjects' true Baseline use of rescue medication. Imputation of weekly diary data after Week 56 will not be performed.

The electronic diary data are a mix of daily and weekly average pain assessments for the index hip or knee, although the recall assessment period is the past 24 hours for both daily and weekly assessments. A weekly mean score will be calculated from the available daily pain scores. Any missing daily pain scores will be left as missing in the weekly pain score calculated. If there are no non-missing observations then the weekly score will be missing. The Baseline mean will be calculated using the last 3 actual values from the last 7 days of the Initial Pain Assessment Period (IPAP). The weekly pain scores (either calculated from the daily scores when available or directly from the weekly pain assessments) will then be utilized for the multiple imputation, and the LOCF and BOCF imputations in the standard way. Note, for the weekly pain score, a pain score being carried forward with LOCF might not be a visit week assessment (eg, carry forward Week 3 for missing Week 4 data). For the purposes of the imputation analyses, where there is no post-baseline observation available to

0900177ed193781b6561Approved\Approved On: 08-10-2019 08:56 (GMT)

carry forward, then the baseline score carried forward will be the baseline average pain score, being the mean of the last 3 pain scores in the baseline assessment period. If there are less than 3 baseline pain scores then the baseline is calculated over the remaining non-missing values.

Missing values in standard summaries of AEs, lab values, vital signs and ECGs will be handled per Pfizer standard algorithms. For the analysis of NIS the Baseline observation will not be carried forward in the case where a post-baseline observation is not available for the LOCF imputation.

